## 6.9 Major investigation items

The following events should be evaluated as major investigation items in this survey.

- [1] Peripheral edema and edema-related events
 

Information will be collected about the presence/absence of events related to peripheral edema and the course of patients before and after the onset of events. The situations on development of these events will be analyzed by means of factor analysis, including analysis of the site affected, dose of the product, concomitant therapy, background variables, etc. The package insert gives precautions on congestive heart failure in patients presenting symptoms related to edema. In 30 overseas placebo-controlled studies, the incidence of hypertension and dyspnea was higher in the patients developing peripheral edema than in patients free of peripheral edema, although the incidence of the other events did not differ markedly between these two groups. In view of these facts, information on cardiac function and the incidence of adverse events of the respiratory system will be also collected.
- [2] Dizziness, somnolence, loss of consciousness, syncope and potential for accidental injury
 

Information will be collected about the presence/absence of events related to dizziness, somnolence, loss of consciousness, syncope and potential for accidental injury and the course of patient's condition before and after the onset of events. The situations on development of these events will be analyzed by factor analysis, including analysis of the dose of the product, concomitant therapy, background variables and so on.
- [3] Vision-related events
 

Information will be collected about the presence/absence of events related to the eyes and the course of patient's condition before and after the onset of events. The situations on development of the events will be analyzed by factor analysis, including analysis of the dose of the product, concomitant therapy, background variables and so on.

Patients developing adverse events included in the major investigation items will be

separately investigated in detail if the sponsor deems it necessary.

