### 7.2 Methods of analysis

#### 7.2.1 Safety analysis

In the safety analysis set, the status of onset of adverse reactions and incidence of adverse reactions (percentage of patients developing adverse events for which the causal relationship with the product cannot be ruled out) will be set as primary analysis items. The factors affecting the incidence of adverse reactions will be also analyzed, for example, the incidence of adverse events will be summarized for each of the factors including background variable.

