8.2.3. Safety analysis

8.2.3.1. Adverse reactions

- All adverse reactions**

Number and proportion of patients with adverse reactions will be tabulated by SOC and PT.

- Serious adverse reactions**

Number and proportion of patients with serious adverse reactions will be tabulated by SOC and PT.

- Details of adverse reactions**

Number and proportion of patients with adverse reactions will be tabulated by SOC and PT for each of the following items.

- Seriousness [Serious, non-serious]
- Expected/unexpected [expected, unexpected]
- Number of days to onset [≤ 4 weeks, >4 to ≤ 13 weeks, >13 weeks]
- Action taken [discontinuation, dose interruption or reduction, dose increase]
- Outcome [not recovered, recovered with sequelae, recovering, resolved/recovered, unknown]

If the same adverse reaction (the same PT) occurs more than once in the same patient, tabulation of the number of patients experiencing the adverse reactions will be handled as follows.

- Seriousness: Serious if both serious and non-serious reactions occurred
- Expected/unexpected: Unexpected if both expected and unexpected reactions occurred
- Number of days to onset: Number of days to onset of the first reaction
- Action taken: If more than one action were taken, select one action in the following order of priority: discontinuation, dose interruption or reduction, dose increase, none
- Outcome: Outcome of the reaction lastly occurred in the patient

- Major investigation items**

Number and proportion of patients will be calculated for the following major investigation items.

- Peripheral edema and edema-related events*^a
*: Adverse events of the cardiovascular and respiratory systems will also be checked.
- Dizziness, somnolence, loss of consciousness, syncope, and potential for accidental injury
- Vision-related events

Furthermore, number and proportion of patients with major investigation items will be tabulated for each SOC and PT by seriousness, action taken and outcome.

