For “peripheral edema and edema-related events”, number and proportion of patients with events will be tabulated by presence or absence of weight increase. Two types of definitions of patients with weight increase are used: 1) those with “weight increased (MedDRA PT)” reported as an adverse reaction; 2) those with body weight increased by 7% or more from baseline at least once. Number and proportion of patients with adverse reactions will be tabulated for each SOC and PT by presence or absence of peripheral edema. In addition, number and proportion of patients with the following adverse reactions will be tabulated by presence or absence of peripheral edema to evaluate the relationship between peripheral edema and cardiovascular and respiratory events.

- Events coded to the MedDRA PT “arrhythmia”, “atrial fibrillation”, “cardiovascular disorder”, “cardiac failure congestive”, “hypertension”, “hypotension”, “palpitations”, “tachycardia”, or “dyspnoea”
- Events coded to the MedDRA SOC “Cardiac disorders”, “Vascular disorders”, or “Respiratory, thoracic and mediastinal disorders”

For “dizziness, somnolence, loss of consciousness, syncope, and potential for accidental injury”, number of days to onset will be tabulated using more specific categories (≤ 4 weeks [1 to 28 days], 1 to 7 days, 8 to 14 days, 15 to 21 days, 22 to 28 days; >4 weeks [≥ 29 days], >4 to ≤ 13 weeks, >13 weeks). In addition, number and proportion of patients with adverse reactions will be tabulated by factor specified in Section 5.4. Tests specified in Section 8.1.3 will be performed to evaluate the relationship between patient demographics, etc. and development of adverse reactions.

Moreover, the median number of days to onset will be tabulated for the following adverse reactions.

- Dizziness
- Somnolence

^a: Occurrence of cardiovascular and respiratory events will be examined in patients with peripheral edema and edema-related events.

- Peripheral edema and edema-related events
- **Pancreas-related events, thyroidal function-related events, change in appetite and activity-related events, suicide-related events, withdrawal symptom and rebound phenomenon-related events, and skin disorder-related events**

Number and proportion of patients will be calculated for each event.

- **Patients with special background**

Number and proportion of patients with adverse reactions and serious adverse reactions will be calculated by SOC and PT in the following subgroups and other patients.

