- Elderly patients
- Pediatric patients
- Patients with renal impairment
- Patients with hepatic impairment

Patients with renal impairment are defined as those with “Renal impairment: yes” or creatinine clearance of less than 60 mL/min.

- **Relationship between dosage and administration and development of adverse reactions**

In order to evaluate the relationship between dosage and administration and development of adverse reactions, number and proportion of patients with adverse reactions will be tabulated by SOC and PT for patients whose creatinine clearance and the initial daily dosage are ≥ 60 mL/min and 150 mg, respectively, and patients whose creatinine clearance and the initial daily dosage are ≥ 30 to < 60 mL/min and 75 mg, respectively.

- **Relationship between prior and concomitant medications and development of adverse reactions**

In order to evaluate the relationship between the drug class of prior or concomitant medications and adverse reactions, number of patients with adverse reactions will be tabulated for each PT by target disease (i.e., diagnosis of neuropathic pain) and drug class of prior or concomitant medications. However, concomitant medications used after the initial onset of the event will be excluded from tabulation. For target disease, diseases with number of patients analyzed of approx. 100 or more will be examined.

- **Occurrence of adverse reactions by inclusion in/exclusion from the safety analysis set**

A listing of adverse reactions in patients excluded from the safety analysis set will be prepared. Moreover, number of patients with adverse reactions will be tabulated by SOC and PT.

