8.2.3.4. Subgroup analysis

Number and proportion of patients with at least one adverse reaction will be tabulated by factor specified in Section 5.4. Tests specified in Section 8.1.3 will be performed to evaluate the relationship between patient demographics, etc. and development of adverse reactions. Furthermore, risk ratio and risk difference for the incidence of adverse reactions and their 95% confidence intervals will be calculated between subgroups.

In addition, number and proportion of patients with adverse reactions in each subgroup will be tabulated by SOC and PT for factors showing a significant difference by testing to evaluate the relationship between patient demographics, etc. and development of adverse reactions. Moreover, patient demographics, etc. (including breakdown of past medical history and complications, prior and concomitant medications) will be tabulated in each subgroup and number and proportion of patients with serious adverse reactions will be tabulated by SOC and PT in each subgroup as necessary.

Laboratory parameters will be tabulated as specified in Section 8.2.3.3 in patients whose target disease is painful diabetic neuropathy.

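### The protocol commits all three major investigation items to analysis by factor, but the SAP specifies the Section 5.4 factor table only for dizziness/somnolence; grouped edema and vision events are not tabulated by those factors

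*SAP*

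**What the plan says.** **Protocol.** Section 6.9 gives each of the three items its own by-factor commitment. For edema: "The situations on development of these events will be analyzed by means of factor analysis, including analysis of the site affected", followed by dose, concomitant therapy and background variables. For vision: "The situations on development of the events will be analyzed by factor analysis, including analysis of the dose of the product", followed by the same two further elements. The dizziness/somnolence item has nearly identical wording. The term factor analysis is not defined. Section 7.2.1 offers as an example that "the incidence of adverse events will be summarized for each of the factors including background variable".

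**SAP 8.2.3.1, all three items.** Each gets an overall count and proportion, and then "number and proportion of patients with major investigation items will be tabulated for each SOC and PT by seriousness, action taken and outcome".

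**SAP 8.2.3.1, dizziness/somnolence.** Only the paragraph on this item continues "In addition, number and proportion of patients with adverse reactions will be tabulated by factor specified in Section 5.4" and "Tests specified in Section 8.1.3 will be performed to evaluate the relationship between patient demographics, etc. and development of adverse reactions".

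**SAP 8.2.3.1, edema.** Grouped edema is also tabulated by weight increase. All reactions, and selected cardiovascular and respiratory reactions, are tabulated by whether peripheral edema was present. Edema also appears to belong to the list of reactions for which median days to onset is given, although the layout of the text is broken there.

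**SAP 8.2.3.1, vision.** There is no further analysis specific to vision.

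**SAP 8.2.3.4.** The Section 5.4 factors are applied to patients with any adverse reaction. Tables by SOC and PT within subgroups follow only "for factors showing a significant difference by testing to evaluate the relationship between patient demographics, etc. and development of adverse reactions".

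**The concern.** Edema and vision are two of the survey's three pre-named safety questions, and the protocol treats all three alike. The SAP carries the by-factor commitment through for one of them and gives no reason for leaving out the other two.

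For many factors, the only route by which an edema or vision result can appear is through a test on a different outcome, namely any adverse reaction. That outcome mixes the item with everything else patients report, so an effect confined to one item is diluted. A factor that matters for edema or vision alone can fail the screen, and the reports would then show no edema or vision incidence by that factor. The listing of major-item reactions in SAP Section 9 shows events but gives no incidence by factor.

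**Working it through.** **1. Scope of the by-factor sentence.** Its wording refers to adverse reactions in general, so it could be read as any reaction. Three things tie it to dizziness/somnolence: it sits in that item's paragraph; the any-reaction table is specified separately in 8.2.3.4; and the version 7.0 entry in the SAP's change log records a by-factor table added for that item and names no other. On the literal reading, edema and vision would still have no table.

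**2. What other tables supply without a screen.**

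| Element in Protocol 6.9 | Unscreened SAP table | Level |
|---|---|---|
| Dose | Creatinine-clearance/initial-dose groups (8.2.3.1); initial dose (8.2.3.5) | SOC and PT |
| Concomitant therapy | Drug class by target disease (8.2.3.1): "number of patients with adverse reactions will be tabulated for each PT by target disease" | PT, counts only |
| Background | Elderly, pediatric, renal, hepatic (8.2.3.1); target disease (8.2.3.5) | SOC and PT |
| Site (edema only) | None as such; only where a PT names a site | PT |

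None of these counts patients with the grouped item. PT rows cannot be summed to patients, because one patient can have two terms. A SOC row may approximate grouped vision incidence if the vision terms fall mainly in one SOC. That is an assumption, since item membership is defined in a risk management plan outside these documents. It works less well for edema. SAP 8.2.3.5 also limits reporting of exploratory results to those that aid interpretation.

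**3. Factor count.** SAP Appendix 2 has 18 factor rows.
- Seven have some unscreened table: hepatic impairment, renal impairment, the three-group age split, target disease, prior medication, concomitant medication and starting dose. 18 - 7 = 11.
- Two of the 11 (six age bands, four creatinine-clearance bands) are finer cuts of factors already partly covered. 11 - 2 = 9.
- The nine are sex, inpatient status, body weight, hemodialysis, past history, complications, non-medication therapy, timing and maximum dose. Hemodialysis overlaps renal impairment, hence *about* nine.

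**4. The plan's own figures.** 1 - 0.999^3400 = 0.967 (stated 97%). 380/5134 = 7.40%, with exact lower 95% limit 6.70%. 3400 x 0.0670 = 227.8 (stated 227 or more). All reproduce, and events are numerous enough for a by-factor table.

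**5. Illustration of the screen.** From the documents: N = 3400, vision 7.40%, two-sided 5%. Assumed: 20% exposed (680 v 2720), risk ratio (RR) 1.5, other reactions at 20% or 28%, independence.

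Item rates: unexposed 0.0740/(0.8 + 0.2 x 1.5) = 6.73%; exposed 1.5 x 6.73% = 10.09%.

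Any reaction = 1 - (1 - item)(1 - other). With other reactions at 20%: 25.4% v 28.1%. At 28%: 32.8% v 35.3%.

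Power is approximately Phi[(d - 1.96 x SE0)/SE1], where d is the difference in proportions, SE0 the pooled and SE1 the unpooled standard error.

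| Scenario | Direct test on item | Any-reaction screen (other reactions 20% / 28%) |
|---|---|---|
| Vision 7.40%, item-only effect | 82% | 30% / 23% |
| Same, other reactions RR 1.1 | 82% | 66% / 68% |
| Same, other reactions RR 1.2 | 82% | 90% / 95% |
| Item-only, 10% exposed | 63% | 21% / 16% |
| Item-only, 50% exposed | 91% | 35% / 26% |
| Item rate 2% (assumed), item-only | 35% | 7% / 6% |
| Edema 12% (assumed), item-only | 96% | 60% / 48% |

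Protocol Section 3 expects vision to be the least frequent item, so edema at 7.40% or above is consistent with the plan. The 12% is an assumption.

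**6. What a descriptive table would show in the first scenario.** Expected events are 680 x 0.1009 = 68.6 and 2720 x 0.0673 = 183.0. SE(log RR) = sqrt(0.8991/68.6 + 0.9327/183.0) = 0.135. The 95% interval around RR 1.5 is exp(0.405 ± 1.96 x 0.135), about 1.15 to 1.95.

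**The case against.** The strongest reply is that the commitment is already partly met. Protocol 6.9 does not cite Section 5.4, require grouped counts or ask for tests, and 7.2.1 gives the by-factor summary only as an example. Dose, concomitant therapy and background each have at least one unscreened table in which edema and vision terms will appear, and most of those tables have SOC rows. This stands. A reader might infer that the SAP contains nothing by factor for edema or vision, or that the protocol promised every Section 5.4 factor with tests; the documents support neither. What remains is the absence of grouped incidence and about nine factors reachable only through the screen.

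A second reply is that the contrast of 82% with 23-30% compares two tests, while the change proposed below is descriptive. That is also right: the contrast measures how weak the screen is as a route to reporting, not the power that the change would deliver. The result also depends on the item rate. The 7.40% comes from clinical studies, and at an assumed 2% even a direct test has only about 35%.

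A third reply is that SAP 4.1 declares testing exploratory, 4.2 sets no decision rule and 8.2.3.5 allows additional analyses. This limits the consequence, but it does not explain why one of three parallel commitments was specified and two were not.

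**Conclusion.** The point holds as a gap between protocol and SAP that should be closed. Followed exactly, the SAP yields no incidence of grouped edema or grouped vision events by any Section 5.4 factor, and for about nine factors even the individual terms appear only after a significant any-reaction test. The gap is clearest for vision, which has no tailored analysis.

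The loss is confined to factors acting mainly on one item. Under the stated assumptions the screen finds such a factor for vision with probability 23-30% at the 7.40% rate, and about 6-7% at an assumed 2%. If the factor also raises other reactions by RR 1.2, the screen has 90-95% and loses nothing. Exposure share, risk ratios, the rate of other reactions and independence are all assumed.

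A reader might infer that edema or vision safety as a whole would go unreported. It would not: the overall incidence of each item, and its seriousness, action taken and outcome, are unaffected.

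**What to change.** In SAP 8.2.3.1, take the by-factor sentence out of the dizziness/somnolence paragraph and make it a separate paragraph covering all three items, for example:

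> For each major investigation item, patients with one or more such adverse reactions will be counted and their incidence given at each level of every Section 5.4 factor, with risk ratios, risk differences and 95% confidence intervals against the Appendix 2 reference category. For target disease and pregnant women, incidence only will be given.

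Also:

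- **Reference category.** Appendix 2 prints *None* for eight yes/no factors. State whether this means the *No* category; otherwise those eight risk ratios could be read as not required.
- **Tests.** Keep the Section 8.1.3 tests for dizziness/somnolence. For edema and vision report estimates with intervals; any tests are exploratory under Section 4.1.
- **Site of edema.** State that site is reported from the PT where the PT names one, and is otherwise not analysed.
- **Timing.** The SAP log already records the survey as completed, so label the added tables as specified after data collection.

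**Cost.** No new data: a few sentences and two more runs of a planned table. If tests are added, 2 items x 18 factors = 36 more, with about 36 x 0.05 = 1.8 false positives expected if no factor had an effect.

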4.1. Statistical hypothesis

Because this survey is not a confirmatory investigation, the testing should be considered as exploratory in nature. Unless otherwise specified, the 2-sided testing is performed with a significance level of 5%.

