5.4. Subgroups

Subgroup analyses of safety will be performed for the following patient demographics and other factors.

- Hepatic impairment
- Renal impairment
- Children (<15 years), adults (≥ 15 to < 65 years), elderly (≥ 65 years)
- Age [< 65 years, ≥ 65 to < 70 years, ≥ 70 to < 75 years, ≥ 75 to < 80 years, ≥ 80 to < 85 years, ≥ 85 years]
- Sex [male, female]
- Inpatient/outpatient status at the initial prescription [inpatient, outpatient]
- Body weight at the start of treatment (by sex) [< 40 kg, ≥ 40 to < 50 kg, ≥ 50 to < 60 kg, ≥ 60 kg]
- Name of target disease (i.e., diagnosis of neuropathic pain) [by disease name]
- Hemodialysis [no, yes]
- Creatinine clearance [< 15 mL/min, ≥ 15 to < 30 mL/min, ≥ 30 to < 60 mL/min, ≥ 60 mL/min]
- Past medical history [no, yes]
- Complications [no, yes]
- Prior medications [no, yes]
- Concomitant medications [no, yes]
- Non-medication therapies [no, yes]
- Timing of drug administration (at the start of treatment) [before meal, after meal, other]
- Daily dose (at the start of treatment) [≤ 25 mg, > 25 to ≤ 75 mg, > 75 to ≤ 150 mg, > 150 to ≤ 300 mg, > 300 to ≤ 600 mg, > 600 mg]
- Daily dose (maximum) [≤ 25 mg, > 25 to ≤ 75 mg, > 75 to ≤ 150 mg, > 150 to ≤ 300 mg, > 300 to ≤ 600 mg, > 600 mg]
- Pregnant and parturient women (pregnant)

Subgroup analyses of efficacy will be performed for the following patient demographics and other factors.

- Hepatic impairment
- Renal impairment
- Children (<15 years), adults (≥ 15 to < 65 years), elderly (≥ 65 years)
- Age [< 65 years, ≥ 65 to < 70 years, ≥ 70 to < 75 years, ≥ 75 to < 80 years, ≥ 80 to < 85 years, ≥ 85 years]
- Sex [male, female]

- Inpatient/outpatient status at the initial prescription [inpatient, outpatient]
- Body weight at the start of treatment (by sex) [<40 kg, ≥ 40 to <50 kg, ≥ 50 to <60 kg, ≥ 60 kg]
- Name of target disease (i.e., diagnosis of neuropathic pain) [by disease name]
- Hemodialysis [no, yes]
- Creatinine clearance [<15 mL/min, ≥ 15 to <30 mL/min, ≥ 30 to <60 mL/min, ≥ 60 mL/min]
- Past medical history [no, yes]
- Complications [no, yes]
- Prior medications [no, yes]
- Concomitant medications [no, yes]
- Timing of drug administration (at the start of treatment) [before meal, after meal, other]
- Daily dose (at the start of treatment) [≤ 25 mg, >25 to ≤ 75 mg, >75 to ≤ 150 mg, >150 to ≤ 300 mg, >300 to ≤ 600 mg, >600 mg]
- Daily dose (maximum) [≤ 25 mg, >25 to ≤ 75 mg, >75 to ≤ 150 mg, >150 to ≤ 300 mg, >300 to ≤ 600 mg, >600 mg]

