8.1.3. Analysis of binary data

Frequency and its proportion will be calculated. If the confidence interval of proportion is calculated, a 2-sided 95% confidence interval (exact method) will be calculated.

If the proportion is compared between subgroups, Fisher’s exact test and Cochran-Armitage test (exact method) will be performed for the relationships with nominal scale data and ordinal scale data, respectively, and the risk ratio and risk difference with their 95% confidence intervals will be calculated.

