- Age category at the start of treatment [<65 years, ≥ 65 to <70 years, ≥ 70 to <75 years, ≥ 75 to <80 years, ≥ 80 to <85 years, ≥ 85 years]
- Body weight at the start of treatment (by sex) (continuous data)
- Body weight category at the start of treatment (by sex) [<40 kg, ≥ 40 to <50 kg, ≥ 50 to <60 kg, ≥ 60 to <70 kg, ≥ 70 to <80 kg, ≥ 80 to <90 kg, ≥ 90 to <100 kg, ≥ 100 kg]
- Duration of target disease (i.e., diagnosis of neuropathic pain) (continuous data)
- Severity of target disease (i.e., diagnosis of neuropathic pain) [mild, moderate, severe]
- Name of underlying disease (i.e., primary disease of nerve damage that cause neuropathic pain) [by disease name]
- Hepatic impairment [no, yes (mild, moderate, severe)]
- Renal impairment [no, yes (mild, moderate, severe)]
- Hemodialysis [no, yes]
- Creatinine clearance (continuous data)
- Creatinine clearance category [<15 mL/min, ≥ 15 to <30 mL/min, ≥ 30 to <60 mL/min, ≥ 60 mL/min]
- Past medical history [no, yes]
- Complications [no, yes]
- Past medical history or complications of cardiovascular disorder^a [no, yes]
- Past medical history of angioedema^b [no, yes]
- Past medical history or complications (at the start of treatment): Peripheral edema and edema-related events^c [no, yes]
- Past medical history or complications (at the start of treatment): Dizziness, somnolence, loss of consciousness, syncope, and potential for accidental injury^c [no, yes]
- Past medical history or complications (at the start of treatment): Vision-related events^c [no, yes]
- Concomitant medications (at the start of treatment) [no, yes]
- Concomitant use of analgesics^d (at the start of treatment) [no, yes]

^a: Past medical history or complications coded to the MedDRA SOC “Cardiac disorders” or “Vascular disorders”

^b: Past medical history coded to the MedDRA HLT “angioedemas”

^c: The same definition as the major investigation items

^d: The following analgesics will be considered as candidates and identified: drugs classified as “3 digits, 114 antipyretics, analgesics, and anti-inflammatory agents; 3 digits, 113 antiepileptics” in the drug name data file or drugs classified as “Standardised Drug Groupings (SDG), analgesia producing opioids; ATC 3rd level, N06A (ANTIDEPRESSANTS)” in the WHO-drug dictionary.

- Concomitant use of opioid analgesics^a (at the start of treatment) [no, yes]
- Concomitant use of oxycodone or lorazepam^b (at the start of treatment) [no, yes]

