- Concomitant use of drugs causing angioedema^c (at the start of treatment) [no, yes]
- Concomitant use of thiazolidines^d (at the start of treatment) [no, yes]

• Information on administration of Lyrica

The following information on administration of Lyrica will be tabulated in the safety analysis set.

- Duration of administration [\leq 4 weeks, $>$ 4 to \leq 13 weeks, $>$ 13 weeks]
- Timing of administration (at the start of treatment) [morning, noon, evening, bedtime, other]
- Timing of drug administration (at the start of treatment) [before meal, after meal, other]
- Daily dose (continuous data)
- Daily dose (at the start of treatment) [\leq 25 mg, $>$ 25 to \leq 75 mg, $>$ 75 to \leq 150 mg, $>$ 150 to \leq 300 mg, $>$ 300 to \leq 600 mg, $>$ 600 mg]
- Daily dose (maximum) [\leq 25 mg, $>$ 25 to \leq 75 mg, $>$ 75 to \leq 150 mg, $>$ 150 to \leq 300 mg, $>$ 300 to \leq 600 mg, $>$ 600 mg]
- Daily dose (final) [\leq 25 mg, $>$ 25 to \leq 75 mg, $>$ 75 to \leq 150 mg, $>$ 150 to \leq 300 mg, $>$ 300 to \leq 600 mg, $>$ 600 mg]

Dosing period is from the day of initial dose in the survey to the day of last dose, including period of dose interruption. Daily dose (continuous data) will be calculated as the mean dosage during the entire period in which Lyrica was actually administered to each patient excluding pro re nata (PRN) prescription, and the mean, standard deviation, and mode will be calculated in the safety analysis set.

^a: The following opioid analgesics will be considered as candidates and identified: drugs classified as “Standardised Drug Groupings (SDG), analgesia producing opioids” in the WHO-drug dictionary.

^b: Drugs classified as “7 digits, 8119002 oxycodone hydrochloride hydrate or 1124022 lorazepam” in the drug name data file

^c: The following drugs causing angioedema will be considered as candidates and identified: drugs classified as “4 digits, 6111 penicillins; 3 digits, 254 contraceptives” in the drug name data file or drugs classified as “Standardised Drug Groupings (SDG), non-steroidal anti-inflammatory drugs (NSAIDs); ACT 3rd level, C09A (ACE INHIBITORS, PLAIN), C09B (ACE INHIBITORS, COMBINATIONS), C09C (ANGIOTENSIN II ANTAGONISTS, PLAIN), C09D (ANGIOTENSIN II ANTAGONISTS, COMBINATIONS); ACT 3rd level, B01AD (Enzymes)” in the WHO-drug dictionary.

^d: Drugs with non-proprietary name of pioglitazone in the drug name data file

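### The only planned test of concomitant medication for dizziness/somnolence events is any drug versus none with no time limit, so it is likely to miss an association with a minority sedating class

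*SAP*

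**What the plan says.** Protocol 6.9 promises that events in the dizziness/somnolence group (which also covers loss of consciousness, syncope and accidental injury) will undergo factor analysis, "including analysis of the dose of the product, concomitant therapy, background variables and so on".

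SAP 8.2.3.1 carries this out for the group: "number and proportion of patients with adverse reactions will be tabulated by factor specified in Section 5.4", followed by the tests of 8.1.3. For a yes/no factor that means Fisher's exact test, with risk ratio, risk difference and 95% confidence intervals. Under SAP 4.1 all testing is exploratory, and "the 2-sided testing is performed with a significance level of 5" percent.

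The concomitant-drug factor in the SAP 5.4 safety list is "Concomitant medications [no, yes". It has no class and no time window, whereas the dosing-time and initial-dose factors in the same list are tied to the start of treatment. Protocol 6.3 also records drugs used to treat an adverse event.

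SAP 8.2.2 defines narrower flags, fixed at the start of treatment: "Concomitant use of opioid analgesics^a (at the start of treatment) [no, yes" and "Concomitant use of oxycodone or lorazepam". They are listed only for describing patients by initial-dose subgroup. No adverse-reaction analysis uses them.

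SAP 8.2.3.1 also has a drug-class table. It gives the number of patients per preferred term, by target disease and class of prior or concomitant drug. It leaves out drugs used after first onset and is limited to diseases with about 100 or more patients. No proportion or test is planned. For efficacy, by contrast, SAP 8.2.4.7 plans a response rate by concomitant drug class.

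**The concern.** An any-drug factor puts a patient on an opioid in the same group as a patient on an antihypertensive or a laxative. If only a small class is associated with dizziness or somnolence, its excess is averaged over everyone taking anything, and the tested risk ratio moves towards 1.

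The open time window works the other way. A patient with no concomitant drug who is given one because of the event can be counted as a user, which raises the apparent risk among users. The one tested contrast can thus hide a real association or produce a false one.

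At stake is signal detection on a question that the protocol names. No confirmatory conclusion depends on it.

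**Working it through.** **The plan's own figures.** The sample-size rationale reproduces: 1 − 0.999^3400 = 96.7% (stated 97%); the exact lower 95% limit for 380/5134 is 6.70%; 0.067 × 3400 = 227.8 (stated 227 or more). None of these concerns the power of a factor contrast, and the documents give no figure for that.

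**Inputs.** Two-sided 5% is from SAP 4.1 and the target of 3400 from SAP 2.1. Everything else is assumed: N analysed (3000 or 3400), share on any drug *a*, share on the class *f*, event rate otherwise *p0*, class risk ratio RR, and no effect of other drugs. The 7.4% rate in one row is the documents' vision-related figure, used as a low value.

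**Dilution.** The rate among users of any drug is [(a − f)p0 + f·p0·RR]/a, so the any-versus-none risk ratio is 1 + (f/a)(RR − 1).

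**Power.** Φ[(d − 1.96·se0)/se1] plus the opposite tail, with se0 the pooled and se1 the unpooled standard error of the difference d.

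First row in full:
- Any-drug rate = (0.82 × 0.20 + 0.08 × 0.40)/0.90 = 0.2178; ratio 1.089; d = 0.0178.
- 2700 versus 300 patients: se0 = 0.0250, se1 = 0.0244. Power = Φ(−1.28) + Φ(−2.74) = 10%.
- Opioid yes versus no, 240 at 40% against 2760 at 20%: d = 0.20, se1 = 0.0325. Power is above 99%.

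| N | a | f | p0 | RR | Any-vs-none ratio | Any-vs-none power | Class power |
|---|---|---|---|---|---|---|---|
| 3000 | 90% | 8% | 20% | 2.0 | 1.09 | 10% | >99% |
| 3000 | 80% | 8% | 20% | 2.0 | 1.10 | 18% | >99% |
| 3000 | 90% | 15% | 20% | 1.5 | 1.08 | 10% | >99% |
| 3400 | 70% | 5% | 15% | 2.0 | 1.07 | 12% | >99% |
| 3400 | 70% | 5% | 15% | 1.5 | 1.04 | 7% | 72% |
| 3400 | 85% | 2% | 7.4% | 1.5 | 1.01 | 5% | 25% |
| 3000 | 50% | 8% | 20% | 2.0 | 1.16 | 57% | >99% |
| 3000 | 70% | 20% | 20% | 2.0 | 1.29 | 93% | >99% |
| 3000 | 80% | 30% | 20% | 2.0 | 1.38 | 97% | >99% |

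Using se1 throughout gives 11%, 19% and 10.5% for any-versus-none in the first three rows. Simulated Fisher's exact tests agree with the any-versus-none column to within about 2 percentage points. For class power they give 71% in place of 72%, and 21% in place of 25%.

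**A rare flag.** With 1% use, N = 3000, p0 = 20% and RR 1.5, 30 patients at 30% face 2970 at 20%: se0 = 0.0735, se1 = 0.0840, Φ[(0.10 − 0.1441)/0.0840] = 30% (27% by Fisher simulation).

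**Time window.** Take no true association, 3000 patients, 300 without a drug before any event, and 20% with the event in both groups (60 and 540). If 10% of the 60 are then given a drug for it, 6 patients change group. The rates become 546/2706 = 20.2% and 54/294 = 18.4%, a ratio of 1.10 with nothing behind it. That is as large as the diluted signal in the second row. The 10% is an assumption.

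**The case against.** The strongest reply is that the SAP does look at drug class. The 8.2.3.1 table works per preferred term, so dizziness and somnolence are in it, and it leaves out drugs used after onset. Some denominators may be recoverable, because 8.2.3.5 tabulates demographics by target disease and 8.2.2 includes a breakdown of concomitant drugs, though the level of detail and the time window may differ. This stands in part. A reader might infer that a class association cannot be seen at all, and the documents do not support that. But counts without proportions, split by term and disease, give no risk ratio and no grouped outcome.

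A reader might also infer a breach of the protocol. Protocol 6.9 asks for analysis by concomitant therapy and names no class and no test, so its wording is met. SAP 8.2.3.5 also allows further analyses.

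Nor can the plan be said to hide a drug interaction. Every patient takes the product, so an opioid contrast may reflect the opioid's own effect or the underlying illness.

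The power loss is not general either. It is small when the class is common or fewer patients take anything, as the last three rows of the table show.

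Finally, it is tempting to extend the remedy to edema through the angioedema-drug flag. That flag pools NSAIDs, penicillins, contraceptives, ACE inhibitors and others, and was defined for a different event. The extension is not supported.

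**Conclusion.** The point holds in a limited form. For this item the only tested concomitant-drug contrast is any versus none. It is open to drugs started because of the event, and the start-of-treatment flags already defined in the SAP feed no adverse-reaction analysis. When the class is a small minority of drug users, the planned test is likely to miss an association that a class contrast would often show: 10% to 18% power against above 99% at 8% opioid use and risk ratio 2, with 80% to 90% on any drug. Over all the inputs tried, any-versus-none power runs from about 5% to 97%. These figures rest on assumed shares, rates and risk ratios and on no effect of other drugs; the documents supply none of them. The effect is on exploratory signal detection. The change is worth making because it is cheap and uses variables already defined.

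**What to change.** In the dizziness/somnolence paragraph of SAP 8.2.3.1:

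- Add the 8.2.2 start-of-treatment opioid analgesic flag (no, yes) as a factor: number and proportion, Fisher's exact test, and risk ratio and risk difference with 95% confidence intervals, reference no.
- Add the oxycodone or lorazepam flag in the same way, labelled secondary. It overlaps the opioid flag, leaves other benzodiazepines in the reference group, and will probably be imprecise.
- State what time window the any-drug factor uses.

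In the drug-class table, add denominators and proportions. The exclusion of drugs used after onset applies only to patients with the event, so the denominator needs a matching window; use at the start of treatment is the simplest.

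Report all of this as exploratory associations, not interactions.

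The cost is SAP wording, two more rows on a list of 19 safety factors, and denominators from data already collected. The downside is a few more exploratory tests.
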